## **11 Data Collection and Database management**

### **11.1 Data collection**

All data should be recorded, handled, and stored in a way that allows its accurate reporting, interpretation, and verification.

Designated investigator staff will enter the data required by the protocol into the Electronic Case Report Forms (eCRF). The eCRFs have been built using fully validated secure web-enabled software that conforms to 21 CFR Part 11 requirements, Investigator site staff will not be given access to the EDC system until they have been trained. Automatic validation programs check for data discrepancies in the eCRFs, allow modification and/or verification of the entered data by the investigator staff.

The investigator/designee is responsible for assuring that the data (recorded on CRFs) (entered into eCRF) is complete, accurate, and that entry and updates are performed in a timely manner. The Investigator must certify that the data entered are complete and accurate.

After final database lock, the investigator will receive copies of the participant data for archiving at the investigational site.

All data should be recorded, handled, and stored in a way that allows its accurate reporting, interpretation, and verification.

### **11.2 Database management and quality control**

Novartis personnel (or designated CRO) will review the data entered by investigational staff for completeness and accuracy. Electronic data queries stating the nature of the problem and requesting clarification will be created for discrepancies and missing values and sent to the investigational site via the EDC system. Designated investigator site staff are required to respond promptly to queries and to make any necessary changes to the data.

Concomitant treatments and prior medications entered into the database will be coded using the World Health Organization (WHO) Drug Reference List, which employs the Anatomical Therapeutic Chemical classification system. Medical history/current medical conditions and adverse events will be coded using the Medical Dictionary for Regulatory Activities (MedDRA) terminology.

Randomization codes and data about all study treatment (s) dispensed to the participant and all dosage changes will be tracked using an Interactive Response Technology (IRT). The system will be supplied by a vendor, who will also manage the database. The data will be sent electronically to Novartis (or a designated CRO) at specific timelines.

Each occurrence of a code break via IRT will be reported to the clinical team and monitor. The code break functionality will remain available until study shut down or upon request of Novartis.

Once all the necessary actions have been completed and the database has been declared to be complete and accurate, it will be locked **and the treatment codes will be unblinded** and made available for data analysis. Any changes to the database after that time can only be made after written agreement by Novartis development management.

### **11.3 Site monitoring**

Before study initiation, at a site initiation visit or at an investigator's meeting, a Novartis representative will review the protocol and data capture requirements (i.e., eSource DDE or eCRFs) with the investigators and their staff. During the study, Novartis employs several methods of ensuring protocol and GCP compliance and the quality/integrity of the sites' data. The field monitor will visit the site to check the completeness of participant records, the accuracy of data capture / data entry, the adherence to the protocol and to Good Clinical Practice, the progress of enrollment, and to ensure that study treatment is being stored, dispensed, and accounted for according to specifications. Key study personnel must be available to assist the field monitor during these visits. Continuous remote monitoring of each site's data may be performed by a centralized Novartis CRA organization. Additionally, a central analytics organization may analyze data & identify risks & trends for site operational parameters, and provide reports to Novartis clinical teams to assist with trial oversight.

The investigator must maintain source documents for each participant in the study, consisting of case and visit notes (hospital or clinic medical records) containing demographic and medical information, laboratory data, electrocardiograms, and the results of any other tests or assessments. All information on CRFs must be traceable to these source documents in the participant's file. The investigator must also keep the original informed consent form signed by the participant (a signed copy is given to the participant).

The investigator must give the monitor access to all relevant source documents to confirm their consistency with the data capture and/or data entry. Novartis monitoring standards require full verification for the presence of informed consent, adherence to the inclusion/exclusion criteria, documentation of SAEs, and of data that will be used for all primary variables. Additional checks of the consistency of the source data with the CRFs are performed according to the study-specific monitoring plan. No information in source documents about the identity of the participants will be disclosed.

## **12 Data analysis and statistical methods**

Any data analysis carried out independently by the investigator should be submitted to Novartis before publication or presentation.

### **12.1 Analysis sets**

For each completed cohort, the data analysis will be performed upon final database lock for the cohort, and the results will be reported while the study may be ongoing for subsequent cohorts. For all analysis sets, participants will be analyzed according to the study treatment(s) received.

The full analysis set (FAS) will include all participants who received any study drug. This set will be used for the primary endpoint analysis.

The safety analysis set is defined similarly as the FAS.

The PK analysis set will include all participants with at least one available valid (i.e., not flagged for exclusion) PK concentration measurement, who received any study drug and with no protocol deviations that impact PK data.

The PD (total target) analysis set for biotherapeutic agents will include all participants with available (total target) PD data and no protocol deviations with relevant impact on (total target) PD data.

The IG analysis set for biotherapeutic agents will include all participants with at least one available valid (i.e., not flagged for exclusion) IG concentration measurement, who received any biotherapeutic study drug and with no protocol deviations that impact IG data.

## **12.2 Participant demographics and other baseline characteristics**

Demographic and other baseline data including disease characteristics will be listed and summarized descriptively by treatment group for all participants in the FAS.

Categorical data will be presented as frequencies and percentages. For continuous data, mean, standard deviation, median, minimum, and maximum will be presented.

Relevant medical histories and current medical conditions at baseline will be listed by treatment, participant, system organ class and preferred term.

## **12.3 Treatments**

The Safety set will be used for the analyses below. Categorical data will be summarized as frequencies and percentages. For continuous data, mean, standard deviation, median, 25th and 75th percentiles, minimum, and maximum will be presented.

The duration of exposure in months to each treatment arm as well as dose intensity (computed as the ratio of actual cumulative dose received and actual duration of exposure) and the relative dose intensity (computed as the ratio of dose intensity and planned dose intensity) will be summarized by means of descriptive statistics using the safety set.

Concomitant medications and significant non-drug therapies prior to and after the start of the study treatment will be listed and summarized according to the Anatomical Therapeutic Chemical classification system, by treatment group and for all participants.

## **12.4 Analysis of the primary endpoint(s)**

The primary aim of the study is to demonstrate the effect on cognition of each anti-inflammatory agent vs. placebo, as measured by the NTB response after the 24 week treatment period.

### **12.4.1 Definition of primary endpoint(s)**

The primary endpoint, NTB total score, includes nine validated components: 1-2) Wechsler Memory Scale Visual-Paired Associates immediate and delayed scores; 3-4); Wechsler Memory Scale Verbal-Paired Associates immediate and delayed scores; 5-6) Rey Auditory Verbal Learning Test (RAVLT) immediate and delayed scores; 7) Wechsler Memory Scale

Digit Span; 8) Controlled Word Association Test (COWAT); and 9) Category Fluency Test (CFT). In order to reduce burden on sites and participants, components 1-4 will not be administered in EXPLAIN-AD ([Harrison 2018](#); [Harrison and Caveney 2012](#)).

For each of the remaining five components, a raw score is first converted to a standardized z-score using baseline mean and SD (calculated from all randomized participants with baseline scores), and a total z-score is derived by averaging all resulting z-scores. A change from baseline is calculated as post-baseline z-score minus pre-treatment z-score, whereby a positive change indicates an improvement from baseline.

#### **12.4.2 Statistical model, hypothesis, and method of analysis**

The study research hypothesis is that each investigated anti-inflammatory agent provides an improvement over placebo in NTB response at 24 weeks.

The change from baseline in NTB total z-score will be analyzed using a restricted maximum likelihood (REML)-based mixed model with repeated measurements (MMRM), using FAS dataset. The model will include fixed, categorical effects of treatment, visit, and treatment-by-visit interaction, as well as the continuous fixed covariates of baseline and baseline-by-visit interaction. The model will also adjust for several important baseline prognostic factors, such as age and MMSE score. Unstructured covariance will be used to model within-patient errors, with Kenward-Roger approximation to estimate denominator degrees of freedom. If the unstructured covariance causes model convergence issues, then other simpler covariance structures will be considered. Least squares mean, the associated 2-sided 90% confidence interval and the p-value will be obtained for each treatment at each visit. The primary comparison will be the contrast between active treatment and placebo at 24 weeks. Both cohort-wise and combined cohort analysis (i.e., pooling placebo data across different cohorts) will be performed.

#### **12.4.3 Handling of missing values/censoring/discontinuations**

For an NTB outcome at any visit, if more than three out of five NTB items are missing, the total z-score will not be derived and will be set to missing. Completely missing visits will be handled through the MMRM model, which implicitly imputes missing data under missing at random (MAR) assumption.

Commercially Confidential Information

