## 4.3 Rationale for Objectives (Endpoints)

### Primary Endpoint

The success of each individual agent tested in EXPLAIN-AD will be determined by a positive result on the NTB total score, the primary endpoint of this study. The NTB is a widely accepted and validated test battery that has been used in numerous industry-sponsored clinical drug trials in AD.

The NTB was selected as the primary endpoint of EXPLAIN-AD primarily for the three reasons detailed below:

Firstly, the NTB allows examination of pro-cognitive agent effects using a well-established neuropsychological assessment with psychometric properties suitable for the early stages of AD ([Harrison et al 2007](#)). In comparison, the psychometric limitations of the Alzheimer's Disease Assessment Scale – Cognitive subscale (ADAS-Cog) in participants with early AD are well-recognized ([Karin et al 2014](#)).

Secondly, the NTB is a composite of multiple globally-established neuropsychological tests that provide a thorough assessment of the cognitive domains affected by early AD, in particular, memory, executive function, attention and verbal fluency.

Commercially Confidential Information

Thirdly, the NTB has shown good assay sensitivity to symptomatic treatment effects in AD drug intervention trials where other endpoints have failed ([Karin et al 2014](#); [Gilman et al 2005](#)).

The NTB sub-tests selected for this trial include the Rey Auditory Verbal Learning Test – immediate and delayed recall (RAVLT-I and RAVLT-D), Wechsler Memory Scale – Digit Span (WMDS), Controlled Word Association Test (COWAT) and Category Fluency Test (CFT).

The NTB is administered directly to the participant by a trained test administrator. The total administration time is estimated to take 35 min on average. Scores of each of the individual sub-tests in the NTB are standardized into z-scores and then added up to provide an overall total score for the NTB.

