2.5.4 Sensitivity analyses

To assess the robustness of the primary analysis results, several sensitivity analyses may be explored, using the primary model adjusted for several important baseline prognostic factors, such as age and educational level.

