2.5.5 Supplementary analyses

A supplementary analysis will be performed by averaging the screening and baseline visits to serve as new baseline, the visits at day 57 and Day 85 to serve as new day 85, and the last 2 visits (day 141 and Day 171) to serve as new Day171.

A supplementary analysis may involve estimation of treatment effects and contrasts (anti-inflammatory agent vs. placebo) within subgroups (e.g., MCI or mild AD positive versus negative) if the sample size in the subgroups is sufficient.

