3.2 Secondary endpoint(s)

For the secondary endpoint, PET $^{\text{CCI}}$, a comparison between an investigational agent and placebo will be based on data from approximately 10 participants per arm. Assuming inter-participant variability of 20%-25%, the power to detect statistically significant treatment difference (using 1-sided α =-0.05) is shown in Table 3-2 below. For the 25% true mean reduction in microglial activation due to an anti-inflammatory agent vs. placebo, there is at least 87% power (assuming coefficient of variation is 25% or less).

Table 3-2 Power for treatment comparison using log-transformed PET CCI at week 12

Coefficient of variation (CV)	True mean reduction (active vs. placebo)	α (1-sided)	Power
0.2	30%	5%	99%
0.2	25%	5%	93%
0.2	20%	5%	78%
0.25	30%	5%	93%
0.25	25%	5%	81%
0.25	20%	5%	62%

The assumed sample size is n=20 (10 per arm)

4

Change to protocol specified analyses

The study was CCI stopped. Therefore, the IA planned after 24 patients complete PET TPSO at 24 weeks will not be conducted.

5 Reference

ICH E9(R1) Harmonized Guideline: addendum on estimands and sensitivity analysis in clinical trials to the guideline on statistical principles for clinical trials. Final version on 20 November 2019.

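### At a partial visit the NTB change score contains a fixed offset between components, because the total may rest on two of five tests and need not use the same tests as baseline

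*Protocol*

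**What the plan says.** Five NTB components are administered: RAVLT immediate and delayed, Digit Span, COWAT and CFT. Each is standardized to the baseline mean and SD, and "a total z-score is derived by averaging all resulting z-scores" (Protocol 12.4.1, repeated in SAP 2.5). Then "A change from baseline is calculated as post-baseline z-score minus pre-treatment z-score".

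The missing-data rule in Protocol 12.4.3 and SAP 2.5.3 is that "if more than three out of five NTB items are missing, the total z-score will not be derived and will be set to missing". Three missing is not more than three, so a mean of two components counts as a total. The model is given a role only for visits with nothing on them: "Completely missing visits will be handled through the MMRM model". On the natural reading, a visit with two, three or four components enters the MMRM as fully observed.

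Neither document asks for the same components at baseline and at the visit. The sensitivity analyses in SAP 2.5.4 are described as "using the primary model adjusted for several important baseline prognostic factors, such as age and educational level", so they vary covariates only. SAP 2.5.5 averages neighbouring visits, for example "the last 2 visits (day 141 and Day 171) to serve as new Day171". SAP section 4 records only the cancelled interim analysis. The end of Protocol 12.4.3 is redacted, but SAP 2.5.3 states the same rule with no visible gap and no matching condition.

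**The concern.** A total made from two tests and a total made from five are different quantities. Subtracting one from the other gives a non-zero result even when nothing has changed, unless the participant's baseline mean on the remaining tests happens to equal the baseline mean on all five. Protocol 12.5.1 assigns two components to memory and three to executive function, so a reduced battery can lose one domain altogether.

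Take a participant with memory scores of -1, executive scores of 0 and no true change. The baseline total is (2 × -1 + 3 × 0)/5 = -0.40. A later visit with executive tests only gives 0 - (-0.40) = +0.40; memory tests only gives -1 - (-0.40) = -0.60. Both exceed the trial's target difference of 0.19. At stake is the precision of the primary endpoint and, if tests are skipped selectively and unequally between arms, its freedom from bias.

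**Working it through.** **Plan's own figure.** Inputs from Protocol 12.8.1 and Table 12-1: 36 evaluable per arm, difference 0.19, SD 0.38, one-sided alpha 0.10. Power is 79.9% by the normal approximation and 79.6% by the noncentral t, so the stated 80% is reproduced. The power figures below use the noncentral t.

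**Offset.** Suppose baseline is complete and a set S of k tests is observed later. Then

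recorded change = mean change on S + [baseline mean of S - baseline mean of all five].

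The bracket is the offset. Baseline scores have unit variance by construction. The documents give no correlation between components, so a common value rho of 0.3 to 0.7 is assumed. Then

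SD(offset) = sqrt((1 - rho)(1/k - 1/5)).

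| Tests left | rho 0.3 | rho 0.5 | rho 0.7 |
|---|---|---|---|
| 2 | 0.46 | 0.39 | 0.30 |
| 3 | 0.31 | 0.26 | 0.20 |
| 4 | 0.19 | 0.16 | 0.12 |

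**Does the baseline covariate absorb it?** Under equal correlations the covariance of the bracket with the baseline total is (1 + 4rho)/5 - (1 + 4rho)/5 = 0. The covariate cannot remove it.

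**SD of the recorded change.** If post-baseline variances stay at 1 and the five-test SD is 0.38, the variance is 0.1444 + (1 - rho)(1/k - 1/5). With two tests left this gives SD 0.595 / 0.543 / 0.484 at rho 0.3 / 0.5 / 0.7; with four left, 0.424 / 0.412 / 0.399.

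**Power at 36 per arm, missingness unrelated to profile and arm.** If a share f of visits is affected, the variance is 0.1444 + f(1 - rho)(1/k - 1/5).

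| Tests missing | f = 5% | f = 20% |
|---|---|---|
| Three | 77.5-78.7% | 71.7-76.0% |
| One | 79.2-79.4% | 78.2-79.0% |

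**One visit in the stopped cohort.** SAP 1.1 reports 34 randomized. Assume all are evaluable, 17 per arm. A two-test visit with a 1 SD offset moves its arm mean by 0.458/17 = 0.027 (rho 0.3) or 0.300/17 = 0.018 (rho 0.7). The standard error of the difference is 0.38 × sqrt(2/17) = 0.130, so the shift is 0.21 to 0.14 of a standard error.

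**What bias would need.** Suppose participants whose memory is 1 SD below their executive function lose the memory tests, and the share of such visits differs by 10 percentage points between arms. The offset is 0.40 each, so the bias is 0.10 × 0.40 = 0.04, or 0.04/0.19 = 21% of the target difference. This is an illustration; the documents contain no such rate.

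**What matching does.** Restricting both times to the same tests makes the bracket exactly zero. The SD of the matched change depends on the component retest correlation r, which the documents do not give. Holding the five-test SD at 0.38, the matched two-test variance is 0.840 - 0.75r and the unmatched variance is 0.444 - 0.3rho. They are equal at r = 0.528 + 0.4rho, that is 0.65 / 0.73 / 0.81 at rho 0.3 / 0.5 / 0.7. Above that value matching is more precise; below it, less. For example, at rho 0.7 and r 0.70 the SD is 0.561 matched against 0.484 unmatched, and power with 20% of visits affected is 73.1% against 76.0%.

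**The case against.** The strongest reply is that the problem may hardly arise. On administration, Protocol 4.3 says "The total administration time is estimated to take 35 min on average". Protocol 8.3.1 asks for a trained administrator, the same one across visits, and Protocol 11.3 requires full source verification of primary-variable data. With one test missing, the power loss is 0.2 to 0.4 points at 5% of visits and 0.6 to 1.4 points at 20%. The larger losses need three of five tests missing at one visit in five. This stands, and it limits the point's weight.

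Second, SAP 2.5.5 already averages screening with baseline and Day 141 with Day 171. That dilutes an offset from a single partial visit, but it averages totals, not matched components, and it is supplementary.

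Third, matching may cost precision. This also stands: the gain depends on retest correlations that nobody can read from these documents.

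Fourth, changing the primary derivation after the cohort has stopped carries its own risk, since Protocol Table 6-1 allows statisticians, programmers and data analysts to be unblinded at individual level. This stands and shapes the fix.

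A reader might infer that the primary comparison is biased, or that matching would restore lost power. The documents support neither. Because every component is centred at its baseline mean, the offset averages to zero when missingness is unrelated to profile and arm, and nothing shows that missingness is selective or unequal.

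**Conclusion.** The rule as written lets a participant with no change record a non-zero change on the primary endpoint, and no visible text corrects it. That much follows from the wording alone. The size is conditional: the offset SDs and power figures rest on equal component correlations of 0.3 to 0.7, unit variances after baseline, a complete baseline, a single-visit comparison, and assumed shares of partial visits. Within those limits the expected harm is a modest loss of power, negligible if partial batteries are rare. The exposure to bias is possible but not shown. The case for acting is that matching makes the offset zero and protects against selective missingness at small cost, and that the rule should be settled before the data can influence it. It is a worthwhile correction, not a threat to the trial's validity.

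**What to change.** In SAP 2.5 and 2.5.3, define change at each visit as the mean of component-level changes over components observed at both baseline and that visit. Keep the two-component minimum, applied to matched components; below it, set the visit to missing for the MMRM. Keep the baseline total as covariate.

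In SAP 2.5.4, add an analysis restricted to visits with all five components at both times, and tabulate the number of matched components by arm and visit. If there are no partial visits, the results are unchanged and the table shows it.

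Record the change in SAP section 4 before final database lock, made by staff blinded to treatment. If that blinding cannot be shown, keep the current derivation as primary and report the matched version as a prespecified sensitivity analysis.

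The cost is a few SAP edits and a small programming change, with no new data. Affected change scores rest on fewer tests, a component missing at baseline is lost for all of that participant's visits, and some visits become missing. The five-component analysis should remain a sensitivity analysis: at 36 per arm, dropping 5% of visits leaves 78.0% power and dropping 20% leaves 72.6%, before the MMRM borrows from other visits.
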